5.4.1.2.2. Estimand of Time to Disease Recurrence

Objective: To evaluate disease recurrence in participants treated with guselkumab versus placebo after surgery

Estimand Scientific Question of Interest: What is the difference in time to disease recurrence at the main database lock, and thus considered to have benefited from guselkumab versus placebo?

Study intervention:

- Experimental: Guselkumab ^{CCI} at Week 0 and then ^{CCI} at Week 8, then ^{CCI} thereafter through the end of the total study period.
- Control: Matched placebo CCI at Weeks 0 and 8 and then CCI thereafter through the end of the total study period.

Population: Participants with recent (<49 days) qualifying surgery and no evidence of active Crohn's disease postoperatively.

Variable: The time to disease recurrence (as defined above) or experiencing ICE 1-3 presented below.

CONFIDENTIAL – FOIA Exemptions Apply in U.S.

Summary Measure (Population-level summary): Difference in the time to disease recurrence (as defined above) or experiencing ICE 1-3 presented below between guselkumab group and the placebo group.

Intercurrent events and their corresponding strategies:

The following are the ICEs considered for this study:

Table 10: Intercurrent Events and Corresponding Analysis Strategies for Disease Recurrence at Main Database Lock

Int loc	ercurrent Events (between baseline and main database k)	Analysis Strategy for Intercurrent Events
1.	A CD-related surgery (with the exception of minor procedures such as drainage of a superficial abscess or seton placement, etc.)	Composite Strategy: Participants are considered having disease recurrence if they experience any of these ICEs, prior to main database lock, as
2.	A prohibited change in CD medication (details in Appendix 9 Medications of Special Interest)	reflected in the variable definition.
3.	Discontinuation of study intervention due to lack of efficacy or an AE of worsening CD	
4.	Discontinuation of study intervention due to COVID-19 related reasons (excluding COVID-19 infection)	Treatment Policy: ICE4 and ICE5 will be ignored, and any data observed after the
5.	Discontinuation of study intervention due to reasons other than those in ICE 3 or 4	associated ICE event will be used for the analysis.

Abbreviation: AE=adverse event; CD=Crohn's disease; COVID-19= Coronavirus disease 2019; ICE=intercurrent event

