6.9. Appendix 9 Medications of Special Interest

The following will be considered as prohibited changes in CD medications for the ICE category 2 for all estimands:

- 1. Prohibited medications initiated after Week 0:
- Immunomodulatory agents except for AZA, 6-MP, or MTX (including, but not limited to, 6-thioguanine, cyclosporine, mycophenolate mofetil, tacrolimus, and sirolimus).
- Advanced therapy agents (including, but not limited to, additional TNFα antagonists, antiIL23 medications, natalizumab, ustekinumab, vedolizumab, rituximab).
- All experimental vaccines and medications, including those for CD (including, but not limited to upadacitinib, filgotinib, ozanimod, etrolizumab, and andecaliximab).
- Thalidomide or related agents.
- Total or partial parenteral nutrition
- IV and intramuscular corticosteroids
- Oral corticosteroids dose at a prednisone-equivalent dose above 20 mg/day, or 6 mg/day of budesonide, or 5 mg/day beclomethasone dipropionate.
- Live vaccines
- Participants must not receive guselkumab outside of the protocol or participate in any other clinical study with an investigational agent while in this study. Prior to termination of study participation, participants should complete evaluations for an ED visit.
- 2. Corticosteroids initiated or doses changed based on medical necessity as assessed by the investigator:
- Initiation of oral corticosteroids (including budesonide and beclomethasone dipropionate) due to worsening of CD.
- Increase in the dose of oral corticosteroids (including budesonide and beclomethasone dipropionate) above the baseline dose due to worsening of CD.
- Initiation of oral corticosteroids (including budesonide and beclomethasone dipropionate) due to reasons other than worsening CD for more than 28 days cumulatively between Week 0 and Week 48.
- Increase in the dose of oral corticosteroids (including budesonide and beclomethasone dipropionate) above the baseline dose due to reasons other than worsening of CD for more than 28 days cumulatively between Week 0 and Week 48.
- 3. Immunomodulator agents initiated from Week 0 through Week 48 or doses changed based on medical necessity as assessed by the investigator:
- Initiation of oral 6-MP/AZA due to worsening of CD.
- Initiation of oral, subcutaneous, or intramuscular MTX due to worsening of CD.
- Increase in the dose of oral 6-MP/AZA above the baseline dose due to worsening of CD.

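### Appendix 9 stops counting immunomodulator starts at Week 48, although ICE 2 defines disease-recurrence events up to the main database lock

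*SAP*

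**What the plan says.** SAP Appendix 9 (section 6.9) opens with its scope: "The following will be considered as prohibited changes in CD medications for the ICE category 2 for all estimands". Its time windows then differ by item.

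- Item 1 has no upper limit: "Prohibited medications initiated after Week 0". It exempts AZA, 6-MP and MTX.
- Item 2, oral steroids for worsening disease, has no Week 48 limit: "Initiation of oral corticosteroids (including budesonide and beclomethasone dipropionate) due to worsening of CD". The matching bullet on dose increases has none either.
- Item 2, oral steroids for other reasons, is limited. Starts count when "due to reasons other than worsening CD for more than 28 days cumulatively between Week 0 and Week 48", and increases when "above the baseline dose due to reasons other than worsening of CD for more than 28 days cumulatively between Week 0 and Week 48".
- Item 3, AZA/6-MP/MTX, reads "Immunomodulator agents initiated from Week 0 through Week 48 or doses changed based on medical necessity as assessed by the investigator".
- Item 4, antibiotics for worsening disease, has no Week 48 limit.

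SAP Table 10 (section 5.4.1.2.2), for time to disease recurrence, points to Appendix 9 for ICE 2 and takes the intercurrent-event window from baseline to the main database lock: "Participants are considered having disease recurrence if they experience any of these ICEs, prior to main database lock". SAP section 1.2.1 estimates follow-up to that lock at 12 to 30 months.

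**The concern.** One list serves estimands with different horizons. A Week 48 limit suits the Week 48 binary endpoints and time to recurrence of symptoms, which is defined through Week 48. It does not suit an endpoint designed to use all follow-up available at the main lock.

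The start of AZA, 6-MP or MTX for worsening disease is the case that matters. Protocol 6.8.1 and SAP 1.2.1 both call it treatment failure, with no Week 48 limit, and Protocol 6.8.1 leaves the full criteria to the SAP. As Appendix 9 stands, a participant who starts after Week 48 can stay event-free in the risk set while taking added Crohn's therapy, whereas the same start before Week 48 is an event. Time to disease recurrence is third of six in the fixed sequence at the end of SAP 5.4.1.3, so its result also decides whether tests 4 to 6 are reached.

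**Working it through.** **1. Does any other rule catch a later start?** Take a participant who starts azathioprine for worsening disease and continues study drug.

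| Rule | Start at Week 40 | Start at Week 56 |
|---|---|---|
| Appendix 9 item 3 | event | outside the window |
| Appendix 9 item 1 | exempt | exempt |
| Disease-recurrence definition (SAP 5.4.1.1): CDAI, steroid, fistula and abscess components | no immunomodulator component | no immunomodulator component |
| ICE 3, stopping study drug for lack of efficacy | not triggered; Protocol 6.8.2 lets study drug continue | not triggered |

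No other component captures the later start by itself. Inclusion criterion 5 requires these drugs to be stopped before randomisation, so initiation is the main route to on-study use. Item 3's wording ties the window to initiation; whether it also governs dose increases and switches is unclear.

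**2. The plan's own figures.** Inputs from SAP section 3: accrual 25%, 35% and 40% over three 6-month periods, analysis at 30 months, dropout 15% a year, 185 per arm, recurrence 20% versus 10%.

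Mean entry time = 0.25×3 + 0.35×9 + 0.40×15 = 9.9 months, so mean administrative follow-up = 30 − 9.9 = 20.1 months. The SAP says approximately 20.

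Hazard ratio = ln(0.90)/ln(0.80) = 0.472. With exponential times and the rates read at 12 months, 76.2 events are expected. Schoenfeld power = Φ(√(76.2/4) × |ln 0.472| − 1.96) = 90.6%. With the rates read at Week 48, 81.8 events are expected, and Freedman power = Φ(√81.8 × (1 − 0.472)/(1 + 0.472) − 1.96) = 90.0%. The stated figure is 90.0%, so it reproduces.

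**3. Share of follow-up after Week 48.** Week 48 = 336/30.4375 = 11.04 months. Every administrative follow-up is at least 12 months, so all participants pass it.

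- Administrative: (20.1 − 11.04)/20.1 = 9.06/20.1 = 45%.
- With dropout: hazard −ln(0.85)/12 = 0.01354 per month. Mean at-risk time is (1 − e^(−0.01354×11.04))/0.01354 = 10.25 months to Week 48 and 17.46 months in total, so 1 − 10.25/17.46 = 41%.
- With dropout and recurrence events (rates read at Week 48): placebo 1 − 9.22/14.38 = 36%; guselkumab 1 − 9.74/15.90 = 39%.
- With dropout and cross-over censoring: SAP 5.4.1.1 censors participants who cross over for endoscopic recurrence alone. As an illustration, assume that the planned 50% (placebo) and 30% (guselkumab) with endoscopic recurrence all leave at Week 48. Time after Week 48 before this loss is 17.46 − 10.25 = 7.21 months. Placebo: 0.5×7.21/(10.25 + 0.5×7.21) = 26%. Guselkumab: 0.7×7.21/(10.25 + 0.7×7.21) = 33%.

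These shares measure the time over which the narrower rule applies. They do not count affected participants.

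**The case against.** Several points limit the concern, and they stand.

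- Most of ICE 2 continues past Week 48: advanced therapies, parenteral steroids, oral steroids for worsening disease and antibiotics. CD surgery and discontinuation for lack of efficacy also count to the lock. What is left uncovered is an immunomodulator start for worsening disease with none of these.
- The Week 48-limited steroid items concern only courses over 28 days for reasons other than worsening disease. A reader might infer that Crohn's steroid rescue stops counting at Week 48; Appendix 9 puts no such limit on it.
- A reader might infer that 45% of events are lost, or that events the power relies on disappear. The documents do not support this. The 20% and 10% rates are set from prior studies tabulated in SAP Table 5. Almost all of these define recurrence by CDAI or symptoms, only one mentions rescue medical therapy, and no power input rests on immunomodulator starts. About 28 of the 76 expected events (37%) fall after Week 48, and using only events to Week 48 would give about 74 to 77% power (Schoenfeld). That would apply only if every component stopped there, which is not so.
- The rule is the same in both arms, and no direction of bias is shown.
- SAP section 1 says only four participants were enrolled and keeps the planned analyses for reference.

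None of this removes the conflict between Appendix 9's stated scope and Table 10's window.

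**Conclusion.** The SAP is inconsistent as written. Initiation of AZA, 6-MP or MTX for worsening disease counts as disease recurrence through Week 48 and then stops counting, while Table 10 runs ICE 2 to the main database lock and the treatment-failure statements carry no Week 48 limit. The SAP gives no reason for the change.

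The exposed period is about 45% of administrative follow-up, or 36 to 39% of at-risk time after dropout and recurrence events, and less after cross-over censoring. These figures rest on the plan's accrual, dropout and event rates with exponential times. The effect on event counts, the hazard ratio or power cannot be sized, because the documents give no frequency for these starts. With four participants enrolled and no confirmatory test to be run, present impact is nil. The point matters if the text is reused.

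**What to change.** In Appendix 9 item 3, state the window by estimand: through Week 48 for the Week 48 endpoints and for time to recurrence of symptoms, and through the main database lock for time to disease recurrence. Name the symptom endpoint explicitly, because SAP 5.4.1.2.4 borrows its intercurrent events from Table 10 although the endpoint runs only through Week 48.

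In the same item, say whether the window also covers dose increases and switches between agents. Separately, say whether the two 28-day steroid bullets for reasons other than worsening disease are meant to apply to Table 10. No particular 28-day rule for longer follow-up is proposed here; that is the sponsor's choice.

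The cost is SAP wording. Protocol 6.8 already records the name, start and stop dates and reason for each concomitant therapy to the last study visit, which is enough to identify later starts. It does not list dose, so counting immunomodulator dose increases would first need confirmation that dose is captured.

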6.10. Appendix 10 Laboratory Toxicity Grading

The grading scale use for lab assessments is based on 'Common Terminology Criteria for Adverse Events (CTCAE) v5.0'.

If a laboratory value falls within the grading as specified below but also within the local laboratory normal limits, the value is considered to be normal and will be reset to grade 0.

Pre-baseline measurements will use the same grading ranges as applied to baseline measurements. In case a test has two sets of ranges – one for baseline normal and one for baseline abnormal, the one for baseline normal will be applied for all measurements taken pre-baseline and on baseline.

Text in gray italic in the table is present in the grading scale, but is not applied by Janssen when grading lab data.

CTCAE Term	Grade 1	Grade 2	Grade 3	Grade 4	Janssen implementation notes
Blood and lymphatic syst	em disorders	-			
Anemia	Hemoglobin (Hgb) <lln -="" 10.0="" dl;
<lln -="" 6.2="" l;
<lln -="" 100="" g="" l<="" td="">Hemoglobin (Hgb) <10.0 - 8.0 g/dL; <6.2 - 4.9 mmol/L; <100 - 80g/L	Hemoglobin (Hgb) <8.0 g/dL; <4.9 mmol/L; <80 g/L; transfusion indicated	Life-threatening consequences; urgent intervention indicated	Clinical signs and symptoms are not taken into consideration for grading.	</lln></lln></lln>	Hemoglobin (Hgb) <10.0 - 8.0 g/dL; <6.2 - 4.9 mmol/L; <100 - 80g/L	Hemoglobin (Hgb) <8.0 g/dL; <4.9 mmol/L; <80 g/L; transfusion indicated	Life-threatening consequences; urgent intervention indicated	Clinical signs and symptoms are not taken into consideration for grading.
Leukocytosis	-	-	>100,000/mm3; >100 x 10e9 /L	Clinical manifestations of leucostasis; urgent intervention indicated	Clinical signs and symptoms are not taken into consideration for grading; Added ranges in SI unit (x 10e9 /L)
Investigations					
Activated partial thromboplastin time prolonged	>ULN - 1.5 x ULN	>1.5 - 2.5 x ULN	>2.5 x ULN; bleeding	-	Clinical signs and symptoms are not taken into consideration for grading.
Alanine aminotransferase increased	>ULN - 3.0 x ULN if baseline was normal; 1.5 - 3.0 x baseline if baseline was abnormal	>3.0 - 5.0 x ULN if baseline was normal; >3.0 - 5.0 x baseline if baseline was abnormal	>5.0 - 20.0 x ULN if baseline was normal; >5.0 - 20.0 x baseline if baseline was abnormal	>20.0 x ULN if baseline was normal; >20.0 x baseline if baseline was abnormal	Ranges defined for "abnormal baseline" are applied only if baseline > ULN. If baseline < LLN, then ranges for "normal baseline" are applied.
Alkaline phosphatase increased	>ULN - 2.5 x ULN if baseline was normal; 2.0 - 2.5 x baseline if baseline was abnormal	>2.5 - 5.0 x ULN if baseline was normal; >2.5 - 5.0 x baseline if baseline was abnormal	>5.0 - 20.0 x ULN if baseline was normal; >5.0 - 20.0 x baseline if baseline was abnormal	>20.0 x ULN if baseline was normal; >20.0 x baseline if baseline was abnormal	Ranges defined for "abnormal baseline" are applied only if baseline > ULN. If baseline < LLN, then ranges for "normal baseline" are applied.
Aspartate aminotransferase increased	>ULN - 3.0 x ULN if baseline was normal; 1.5 - 3.0 x baseline if baseline was abnormal	>3.0 - 5.0 x ULN if baseline was normal; >3.0 - 5.0 x baseline if baseline was abnormal	>5.0 - 20.0 x ULN if baseline was normal; >5.0 - 20.0 x baseline if baseline was abnormal	>20.0 x ULN if baseline was normal; >20.0 x baseline if baseline was abnormal	Ranges defined for "abnormal baseline" are applied only if baseline > ULN. If baseline < LLN, then ranges for "normal baseline" are applied.

CTCAE Term	Grade 1	Grade 2	Grade 3	Grade 4	Janssen implementation notes
Blood bilirubin increased	>ULN - 1.5 x ULN if baseline was normal; > 1.0 - 1.5 x baseline if baseline was abnormal	>1.5 - 3.0 x ULN if baseline was normal; >1.5 - 3.0 x baseline if baseline was abnormal	>3.0 - 10.0 x ULN if baseline was normal; >3.0 - 10.0 x baseline if baseline was abnormal	>10.0 x ULN if baseline was normal; >10.0 x baseline if baseline was abnormal	Ranges defined for "abnormal baseline" are applied only if baseline > ULN. If baseline < LLN, then ranges for "normal baseline" are applied.
CD4 lymphocytes	<lln -="" 500="" mm3;<="" td=""><500 - 200/mm3;	<200 - 50/mm3;	<50/mm3;		</lln>	<500 - 200/mm3;	<200 - 50/mm3;	<50/mm3;	
decreased	<lln -="" 0.5="" 10e9="" l<="" td="" x=""><0.5 - 0.2 x 10e9 /L	<0.2 x 0.05 - 10e9 /L	<0.05 x 10e9 /L		</lln>	<0.5 - 0.2 x 10e9 /L	<0.2 x 0.05 - 10e9 /L	<0.05 x 10e9 /L	
Cholesterol high	>ULN - 300 mg/dL; >ULN - 7.75 mmol/L	>300 - 400 mg/dL; >7.75 - 10.34 mmol/L	>400 - 500 mg/dL; >10.34 - 12.92 mmol/L	>500 mg/dL; >12.92 mmol/L	
CPK increased	>ULN - 2.5 x ULN	>2.5 x ULN - 5 x ULN	>5 x ULN - 10 x ULN	>10 x ULN	
Creatinine increased	Creatine Kinase >ULN - 1.5 x ULN	Creatine Kinase >1.5 - 3.0 x baseline; >1.5 - 3.0 x ULN	Creatine Kinase >3.0 x baseline; >3.0 - 6.0 x ULN	Creatine Kinase >6.0 x ULN	
Fibrinogen decreased	<1.0 - 0.75 x LLN; if abnormal, <25% decrease from baseline	<0.75 - 0.5 x LLN; if abnormal, 25 - <50% decrease from baseline	<0.5 - 0.25 x LLN; if abnormal, 50 - <75% decrease from baseline	<0.25 x LLN; if abnormal, 75% decrease from baseline; absolute value <50 mg/dL	Ranges defined for "abnormal" are applied only on values < LLN. Grade 0 will be assigned to values > ULN.
GGT increased	>ULN - 2.5 x ULN if baseline was normal; 2.0 - 2.5 x baseline if baseline was abnormal	>2.5 - 5.0 x ULN if baseline was normal; >2.5 - 5.0 x baseline if baseline was abnormal	>5.0 - 20.0 x ULN if baseline was normal; >5.0 - 20.0 x baseline if baseline was abnormal	>20.0 x ULN if baseline was normal; >20.0 x baseline if baseline was abnormal	Ranges defined for "abnormal baseline" are applied only if baseline > ULN. If baseline < LLN, then ranges for "normal baseline" are applied.
Haptoglobin decreased	<lln< td="">-	-	-		</lln<>	-	-	-	
Hemoglobin increased	Increase in >0 - 2 g/dL; Increase in >0 - 20 g/L	Increase in >2 - 4 g/dL; Increase in >20 - 40 g/L	Increase in >4 g/dL; Increase in >40 g/L	-	The increase indicates the level of increase above normal (above ULN). Applied as, e.g. grade 1 (g/dL): >ULN – ULN+2 g/dL; Added ranges in SI unit (g/L).

CTCAE Term	Grade 1	Grade 2	Grade 3	Grade 4	Janssen implementation notes
INR increased	>1.2 - 1.5; >1 - 1.5 x baseline if on anticoagulation; monitoring only indicated	>1.5 - 2.5; >1.5 - 2.5 x baseline if on anticoagulation; dose adjustment indicated	>2.5; >2.5 x baseline if on anticoagulation; bleeding	-	Concomitant therapy or clinical signs and symptoms are not taken into consideration for grading.
Lipase increased	>ULN - 1.5 x ULN	>1.5 - 2.0 x ULN; >2.0 - 5.0 x ULN and asymptomatic	>2.0 - 5.0 x ULN with signs or symptoms; >5.0 x ULN and asymptomatic	>5.0 x ULN and with signs or symptoms	"Asymptomatic" ranges are not taken into consideration for grading, i.e. worst case grading is applied.
Lymphocyte count decreased	<lln -="" 800="" mm3;
<lln -="" 0.8="" 10e9="" l<="" td="" x=""><800 - 500/mm3; <0.8 - 0.5 x 10e9 /L	<500 - 200/mm3; <0.5 - 0.2 x 10e9 /L	<200/mm3; <0.2 x 10e9 /L		</lln></lln>	<800 - 500/mm3; <0.8 - 0.5 x 10e9 /L	<500 - 200/mm3; <0.5 - 0.2 x 10e9 /L	<200/mm3; <0.2 x 10e9 /L	
Lymphocyte count increased	-	>4000/mm3 - 20,000/mm3; >4 - 20 x 10e9 /L	>20,000/mm3; >20 x 10e9 /L	-	Added ranges in SI unit (x 10e9 /L).
Neutrophil count decreased	<lln -="" 1500="" mm3;
<lln -="" 1.5="" 10e9="" l<="" td="" x=""><1500 - 1000/mm3; <1.5 - 1.0 x 10e9 /L	<1000 - 500/mm3; <1.0 - 0.5 x 10e9 /L	<500/mm3; <0.5 x 10e9 /L	Both Neutrophils and segmented neutrophils are graded using these criteria.	</lln></lln>	<1500 - 1000/mm3; <1.5 - 1.0 x 10e9 /L	<1000 - 500/mm3; <1.0 - 0.5 x 10e9 /L	<500/mm3; <0.5 x 10e9 /L	Both Neutrophils and segmented neutrophils are graded using these criteria.
Platelet count decreased	<lln -="" 75,000="" mm3;
<lln -="" 10e9="" 75.0="" l<="" td="" x=""><75,000 - 50,000/mm3; <75.0 - 50.0 x 10e9 /L	<50,000 - 25,000/mm3; <50.0 - 25.0 x 10e9 /L	<25,000/mm3; <25.0 x 10e9 /L		</lln></lln>	<75,000 - 50,000/mm3; <75.0 - 50.0 x 10e9 /L	<50,000 - 25,000/mm3; <50.0 - 25.0 x 10e9 /L	<25,000/mm3; <25.0 x 10e9 /L	
Serum amylase increased	>ULN - 1.5 x ULN	>1.5 - 2.0 x ULN; >2.0 - 5.0 x ULN and asymptomatic	>2.0 - 5.0 x ULN with signs or symptoms; >5.0 x ULN and asymptomatic	>5.0 x ULN and with signs or symptoms	"Asymptomatic" ranges are not taken into consideration for grading, i.e. worst case grading is applied.
White blood cell decreased	<lln -="" 3000="" mm3;
<lln -="" 10e9="" 3.0="" l<="" td="" x=""><3000 - 2000/mm3; <3.0 - 2.0 x 10e9 /L	<2000 - 1000/mm3; <2.0 - 1.0 x 10e9 /L	<1000/mm3; <1.0 x 10e9 /L		</lln></lln>	<3000 - 2000/mm3; <3.0 - 2.0 x 10e9 /L	<2000 - 1000/mm3; <2.0 - 1.0 x 10e9 /L	<1000/mm3; <1.0 x 10e9 /L	
Metabolism and nutrition		- 2.0 X 1009/L	- 1.0 X 1009 /L	<1.0 x 10e9 /L	
Acidosis	pH <normal, but="">=7.3</normal,>	-	pH <7.3	Life-threatening consequences	pH <normal is
implemented as pH <lln. Clinical signs and symptoms are not taken into consideration for grading.</lln. </normal>

CTCAE Term	Grade 1	Grade 2	Grade 3	Grade 4	Janssen implementation notes
Alkalosis	pH >normal, but <=7.5	-	pH >7.5	Life-threatening consequences	pH >normal is implemented as pH >ULN. Clinical signs and symptoms are not taken into consideration for grading.
Hypercalcemia	Corrected serum calcium of >ULN - 11.5 mg/dL; >ULN - 2.9 mmol/L; Ionized calcium >ULN - 1.5 mmol/L	Corrected serum calcium of >11.5 - 12.5 mg/dL; >2.9 - 3.1 mmol/L; Ionized calcium >1.5 - 1.6 mmol/L; Symptomatic	Corrected serum calcium of >12.5 - 13.5 mg/dL; >3.1 - 3.4 mmol/L; Ionized calcium >1.6 - 1.8 mmol/L; hospitalization indicated	Corrected serum calcium of >13.5 mg/dL; >3.4 mmol/L; Ionized calcium >1.8 mmol/L; life-threatening consequences	Clinical signs and symptoms are not taken into consideration for grading. Note: For Hypercalcemia or Hypocalcemia in the CTCAE Lab Toxicity grading scale, the reference ranges from serum calcium (ULN /LLN) from the local or central lab are being utilized.
Hyperkalemia	Potassium >ULN - 5.5 mmol/L	Potassium >5.5 - 6.0 mmol/L; intervention initiated	Potassium >6.0 - 7.0 mmol/L; hospitalization indicated	Potassium >7.0 mmol/L; life-threatening consequences	Clinical signs and symptoms are not taken into consideration for grading.
Hypermagnesemia	Magnesium >ULN - 3.0 mg/dL; >ULN - 1.23 mmol/L	-	Magnesium >3.0 - 8.0 mg/dL; >1.23 - 3.30 mmol/L	Magnesium >8.0 mg/dL; >3.30 mmol/L; life-threatening consequences	Clinical signs and symptoms are not taken into consideration for grading.
Hypernatremia	Sodium >ULN - 150 mmol/L	Sodium >150 - 155 mmol/L; intervention initiated	Sodium >155 - 160 mmol/L; hospitalization indicated	Sodium >160 mmol/L; life-threatening consequences	Clinical signs and symptoms are not taken into consideration for grading.
Hypertriglyceridemia	Triglycerides 150 mg/dL - 300 mg/dL; 1.71 mmol/L - 3.42 mmol/L	Triglycerides >300 mg/dL - 500 mg/dL; >3.42 mmol/L - 5.7 mmol/L	Triglycerides >500 mg/dL - 1000 mg/dL; >5.7 mmol/L - 11.4 mmol/L	Triglycerides >1000 mg/dL; >11.4 mmol/L; life-threatening consequences	Clinical signs and symptoms are not taken into consideration for grading.

CTCAE Term	Grade 1	Grade 2	Grade 3	Grade 4	Janssen implementation notes
Hypoalbuminemia	Albumin <lln -="" 3="" dl;
<lln -="" 30="" g="" l<="" td="">Albumin <3 - 2 g/dL; <30 - 20 g/L	Albumin <2 g/dL; <20 g/L	Life-threatening consequences; urgent intervention indicated	Clinical signs and symptoms are not taken into consideration for grading.	</lln></lln>	Albumin <3 - 2 g/dL; <30 - 20 g/L	Albumin <2 g/dL; <20 g/L	Life-threatening consequences; urgent intervention indicated	Clinical signs and symptoms are not taken into consideration for grading.
Hypocalcemia	Corrected serum calcium of <lln -="" 8.0="" dl;
<lln -="" 2.0="" l;<="" mmol="" td="">Corrected serum calcium of <8.0 - 7.0 mg/dL; <2.0 - 1.75 mmol/L;	Corrected serum calcium of <7.0 - 6.0 mg/dL; <1.75 - 1.5 mmol/L;	Corrected serum calcium of <6.0 mg/dL; <1.5 mmol/L;	Clinical signs and symptoms are not taken into consideration for grading.	</lln></lln>	Corrected serum calcium of <8.0 - 7.0 mg/dL; <2.0 - 1.75 mmol/L;	Corrected serum calcium of <7.0 - 6.0 mg/dL; <1.75 - 1.5 mmol/L;	Corrected serum calcium of <6.0 mg/dL; <1.5 mmol/L;	Clinical signs and symptoms are not taken into consideration for grading.
	Ionized calcium <lln -
1.0 mmol/L</lln>	Ionized calcium <1.0 - 0.9 mmol/L; Symptomatic	Ionized calcium <0.9 - 0.8 mmol/L; hospitalization indicated	Ionized calcium <0.8 mmol/L; life-threatening consequences	Note: For Hypercalcemia or Hypocalcemia in the CTCAE Lab Toxicity grading scale, the reference ranges from serum calcium (ULN /LLN) from the local or central lab are being utilized.
Hypoglycemia	Glucose <lln -="" 55="" dl;
<lln -="" 3.0="" l<="" mmol="" td="">Glucose <55 - 40 mg/dL; <3.0 - 2.2 mmol/L	Glucose <40 - 30 mg/dL; <2.2 - 1.7 mmol/L	Glucose <30 mg/dL; <1.7 mmol/L; life-threatening consequences; seizures	Clinical signs and symptoms are not taken into consideration for grading. Urine glucose is not graded.	</lln></lln>	Glucose <55 - 40 mg/dL; <3.0 - 2.2 mmol/L	Glucose <40 - 30 mg/dL; <2.2 - 1.7 mmol/L	Glucose <30 mg/dL; <1.7 mmol/L; life-threatening consequences; seizures	Clinical signs and symptoms are not taken into consideration for grading. Urine glucose is not graded.
Hypokalemia	Potassium <lln -="" 3.0
mmol/L</lln>	Symptomatic with Potassium <lln -="" 3.0
mmol/L; intervention indicated</lln>	Potassium <3.0 - 2.5 mmol/L; hospitalization indicated	Potassium <2.5 mmol/L; life-threatening consequences	"Symptomatic" ranges are applied for grade 2, grade 1 not assigned, i.e. worst case applied. Clinical signs and symptoms are not taken into consideration for grading of grade 3 and 4.
Hypomagnesemia	Magnesium <lln -="" 1.2="" dl;
<lln -="" 0.5="" l<="" mmol="" td="">Magnesium <1.2 - 0.9 mg/dL; <0.5 - 0.4 mmol/L	Magnesium <0.9 - 0.7 mg/dL; <0.4 - 0.3 mmol/L	Magnesium <0.7 mg/dL; <0.3 mmol/L; life-threatening consequences	Clinical signs and symptoms are not taken into consideration for grading.	</lln></lln>	Magnesium <1.2 - 0.9 mg/dL; <0.5 - 0.4 mmol/L	Magnesium <0.9 - 0.7 mg/dL; <0.4 - 0.3 mmol/L	Magnesium <0.7 mg/dL; <0.3 mmol/L; life-threatening consequences	Clinical signs and symptoms are not taken into consideration for grading.

CTCAE Term	Grade 1	Grade 2	Grade 3	Grade 4	Janssen implementation notes
Hyponatremia Bonal and urinary disord	Sodium <lln -="" 130
mmol/L</lln>	Sodium 125-129 mmol/L and asymptomatic	Sodium 125-129 mmol/L symptomatic; 120-124 mmol/L regardless of symptoms Sodium <130-120 mmol/L	Sodium <120 mmol/L; life-threatening consequences	Clinical signs and symptoms are not taken into consideration for grading. Worst case ("<130-120 mmol/L" for grade 3 added by Janssen) is applied across grade 2/3 ranges: 120-129 mol/L assigned to grade 3, grade 2 not used.
Renal and urinary disord Proteinuria	1+ proteinuria;	Adult:	Adult:	-	In case both 24-h urine
	urinary protein ≥ULN - <1.0 g/24 hrs; urinary protein ≥ULN - <1000 mg/day	2+ and 3+ proteinuria; urinary protein 1.0 - <3.5 g/24 hrs; urinary protein 1000 - <3500 mg/day Pediatric: Urine P/C (Protein/Creatinine) ratio 0.5 - 1.9; Urine P/C (Protein/Creatinine) 56.5 - 214.7 g/mol	4+ proteinuria; urinary protein >=3.5 g/24 hrs; urinary protein >=3500 mg/day; Pediatric: Urine P/C (Protein/Creatinine) ratio >1.9; Urine P/C (Protein/Creatinine) >214.7 g/mol		collection and dipstick are collected, then worst case is taken, as opposed to having 24-h urine collection take precedence over dipstick. Added ranges in SI unit for urinary protein (mg/day) and for urine P/C (g/mol). Pediatric grading is applied to age range [0- 18]. Adult grading is applied for ages [>18].

* Grade 0 is assigned to a lab assessment when the lab test is described in the table, but the lab value is not assigned a grade 1 or higher.

